18.4 Emergency Circumstances

If emergency circumstances unrelated to the study should occur, Thrombolex, Inc. will follow the FDA guidance on how to manage the ongoing investigation during such crisis.³¹

19.0 DEVICE AND DRUG ACCOUNTABILITY

19.1 Bashir™ Endovascular Catheter Packaging for the IR Suite / Cath Lab

The Bashir™ Catheters are packaged to provide protection during transportation and to facilitate introduction into the sterile environment. The shaft of the Bashir Catheter

is inserted into a protective tube, mounted to a 0.3" wide x 46.5" long; .020" HDPE is inserted into a peel-pouch is shipped in a dispenser box.

19.2 Device Accountability

A packing slip will accompany all devices in each shipping box, 1 slip for multiple catheters. The site will retain the packing slips in their regulatory binder. The site should document each device and device disposition on the device accountability log provided to the site by the CRO.

19.3 Drug Accountability

The study drug is commercially available and is to be purchased by the institution. The site should document each vial and drug disposition in the case report form for each study subject.

20.0 STATISTICAL CONSIDERATIONS - ENDPOINTS, HYPOTHESES, AND ANALYTICAL METHODS

20.1 Power and Sample Size Calculation

The study will enroll up to 125 patients with the goal to have 100 evaluable subjects (after accounting for a 20% attrition rate of subjects who are enrolled and treated) in a prospective, non-randomized, multi-center study. The following assumptions were used to determine the required sample size for the study:

- This study would have an attrition rate of subjects enrolled and treated no greater than 20%.
- A mean reduction of 28% in the primary efficacy endpoint (RV/LV diameter ratio) after 48 hours in BEC-treated patients. It will be compared to the performance goal of 20% reduction in RV/LV diameter ratio after 48 hours.
- A standard deviation (SD) on the scale of percent change for the primary efficacy endpoint (RV/LV ratio) of 25%.
- An interim analysis will be conducted once data on 60 participants have been collected, in order to obtain preliminary efficacy results using the primary efficacy endpoint. To constrain the overall type I error rate, an O'Brien-Fleming alpha spending function will be utilized, in which a stringent type I error rate of alpha=0.0038 will be used for the interim analysis, leaving alpha=0.0212 for the final analysis, when study data are complete.

Alpha values for interim and final analyses were obtained from the R package ldbounds function bounds(), which calculates alpha given the type of spending function, timing of the interim analyses, and overall type I error desired. The parameters used to obtain these alpha values were O'Brien-Fleming spending function, single interim analysis at 60% of total sample, and overall alpha of 0.025 (one-sided).

The sample size needed for 80% power to test the primary efficacy hypothesis in the final analysis is 83 subjects, based on the assumptions stated above, and alpha = 0.0212.⁶ This estimate is based on a one-sided one-sample t-test of mean percent change from baseline to 48-hour assessment, comparing the percent change in RV/LV ratio that is predicted in this study with a 20% reduction.

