20.2 Endpoints, Hypotheses, and Analytical Methods

20.2.1 Primary Efficacy Endpoint:

The primary efficacy endpoint is reduction in the chest CT-measured RV/LV diameter ratio assessed by contrast enhanced chest CT from baseline within 48 ± 6 hours of initiation of treatment.

20.2.2 Hypothesis:

The predicate device for Bashir Endovascular Catheter is the EkoSonic Endovascular System (EKOS, Bothell, WA). The SEATTLE II Study reported a reduction in RV/LV diameter ratio of -0.42 ± 0.36 (mean ± SD) in 115 patients who underwent a within-window CT measurement of RV/LV diameter ratio. We hypothesize that RV/LV diameter ratio measured at 48 hours compared with measured ratio at baseline will be reduced on average by more than 20%.

20.2.2.1 Analytical methods: A change score d will be calculated:

$$d = \frac{R_{48} - R_0}{R_0}$$

that expresses the change as a proportion of the baseline value, where R_0 and R_{48} are $\frac{RV}{LV}$ at time 0 and 48 hours post-treatment, respectively. A larger decrease from baseline will result in a change score with a greater magnitude and a negative sign. The change score will be compared to the benchmark value of 20% in a one-sided hypothesis test:

$$H_0: d \geq -0.2$$

$$H_A: d < -0.2$$

The distribution of the change score will be examined to assess whether the normality assumption is met, using both graphical methods (Q-Q plots and histograms) as well as multiple hypothesis tests of normality (Shapiro-Wilk, Kolmogorov-Smirnov, Anderson-Darling, and Cramer-von Mises). Multiple hypothesis testing methods will be employed to assess normality because the choice of the most powerful test depends on the distributional qualities of the data; if the different tests do not result in the same conclusion, more weight will be given to the method that is best suited to the observed distributional qualities of the data (e.g., heaviness of tails). If the data are determined to be normal based on these methods, a t test will be done; if not, a one-sample Wilcoxon

signed rank test (the non-parametric alternative to the one-sample t test) will be done. In addition, the t-test will be presented for the primary endpoint analysis regardless of the normality of the test results.

The test will be performed twice: once at the interim analysis (with $\alpha=0.0038$) and once at the final analysis (with $\alpha=0.0212$). If the p-value is less than α at either analysis, then the test will be considered statistically significant.

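### The final p-value cut-off of 0.0212 is the alpha increment left after the interim, not the nominal final level of the named O'Brien-Fleming design (0.0238 at 60/100); the rule is conservative, with overall error about 0.0225 against the 0.025 intended

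*Combined protocol and SAP*

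**What the plan says.** Section 20.1 sets the interim: "An interim analysis will be conducted once data on 60 participants have been collected". It gives the inputs to the boundary calculation as "O'Brien-Fleming spending function, single interim analysis at 60% of total sample", with overall alpha 0.025, one-sided. The stated result is that "a stringent type I error rate of alpha=0.0038 will be used for the interim analysis, leaving alpha=0.0212 for the final analysis". Both values are attributed to an R function, "which calculates alpha given the type of spending function, timing of the interim analyses, and overall type I error desired". The sample size of 83 for 80% power is then computed at 0.0212.

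Section 20.2.2.1 turns the two values into a decision rule. "The test will be performed twice: once at the interim analysis" at 0.0038, and once at the end at 0.0212. If the p-value is below its alpha "at either analysis, then the test will be considered statistically significant". No separate final boundary or nominal level is given, and neither section says that 0.0212 is meant to be conservative.

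**The concern.** An alpha-spending design yields two different quantities at each look after the first: the alpha spent there (an increment) and the nominal p-value level that spends it. They coincide only at the first look. At the final look the increment counts only trials that cross for the first time, while the nominal level also covers trials that had already crossed at the interim. Because the looks share data, the nominal level is larger than the increment.

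Section 20.2.2.1 uses the increment where the nominal level belongs. The rule is therefore a simple additive split, while 20.1 describes a spending design. At 60/100, a final p-value between 0.0212 and 0.0238 would be a failure under 20.2.2.1 and a success under the design named in 20.1. This is the primary efficacy test of a single-arm study against a performance goal, so the threshold should be settled before final data are seen.

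**Working it through.** **Inputs (20.1).** Overall one-sided alpha 0.025; one interim at 60%, i.e. 60 of 100 evaluable; performance goal 20%, assumed reduction 28%, SD 25, so the standardised effect is 8/25 = 0.32. Cut-offs 0.0038 and 0.0212 (20.1 and 20.2.2.1). Section 20.1 speaks of data on 60 participants; that all 60 are evaluable is an assumption, varied below.

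**1. Reproduce the plan's alphas.** O'Brien-Fleming-type spending at t = 0.6:

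- Spent: 2[1 - Φ(2.2414/√0.6)] = 2[1 - Φ(2.8936)] = 0.003808
- Remaining: 0.025 - 0.003808 = 0.021192

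These round to 0.0038 and 0.0212. The classic O'Brien-Fleming boundary would give about 0.0051 and 0.0232, so it does not explain 0.0212.

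**2. Reproduce N.** Noncentral-t power at 0.0212 is 79.7% for n = 82 and 80.2% for n = 83. N = 83 is right for that level.

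**3. Error of the rule as written.** Overall error = 1 - P(Z1 < 2.669, Z2 < 2.030), bivariate normal with correlation √(n1/N), where 2.669 and 2.030 are the z-values for 0.0038 and 0.0212. At 60/100 the correlation is √0.6 = 0.775 and the error is 0.0225. The probability of first crossing at the final look is 0.0225 - 0.0038 = 0.0187, not 0.0212.

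**4. Nominal final level.** Solving 1 - P(Z1 < 2.669, Z2 < c) = 0.025 at 60/100 gives c = 1.981, a level of 0.0238.

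**5. Other evaluable counts, with 0.0038 kept at the interim.** The 48-subject rows apply the plan's 20% attrition to the first 60.

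| Interim n | Final n | Error with 0.0212 | Final level giving 0.025 |
|---|---|---|---|
| 60 | 83 | 0.0219 | 0.0244 |
| 60 | 90 | 0.0222 | 0.0241 |
| 60 | 100 | 0.0225 | 0.0238 |
| 60 | 110 | 0.0227 | 0.0235 |
| 60 | 125 | 0.0230 | 0.0232 |
| 48 | 100 | 0.0230 | 0.0232 |
| 48 | 125 | 0.0234 | 0.0228 |

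A fixed 0.0238 would give 0.0255 at 60/125 or 48/100 (both are a fraction of 0.48).

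**6. t-tests in place of z-tests (60/100, normal data).** The error is about 0.0226 with 0.0212 and about 0.0251 with 0.0238.

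**7. Cost.** Final-analysis power at n = 100 is 87.2% at 0.0212 and 88.2% at 0.0238. The observed mean reduction needed (SD 25) is 20 + 2.5 × t with 99 degrees of freedom: 25.14% versus 25.01%.

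**The case against.** The strongest reply is that nothing is broken. Section 20.1 says the split serves to constrain the overall error, and lists 0.025 as the error desired. A rule with error 0.0225 meets that limit. The two alphas, their sum and N = 83 all reproduce, and a fixed, pre-specified additive split is a legitimate choice. All of this stands. It means the fault is a conservative boundary with the wrong label, not a breach of the limit and not a slip in the subtraction. It does not remove the mismatch: the plan names one design and applies the cut-off of another, without saying so.

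A reader might infer more than this. One inference is that the type I error is inflated or the sample size wrong; steps 2 and 3 show neither. The opposite inference is that, because 0.0038 + 0.0212 = 0.025, the error can never exceed 0.025. That sum bounds the error only if the test at each look holds its nominal level. Section 20.2.2.1 chooses between a t-test and a signed-rank test after looking at the data, while the hypothesis in 20.2.2 concerns the average reduction. As an illustration only: suppose Shapiro-Wilk p < 0.05 triggers the signed-rank test (the plan gives no threshold) and the true mean lies exactly at the goal. Simulation of the two-look rule (20,000 replicates, 60/100) then gives about 0.024 with normal data, 0.045 with right skewness 0.5 and 0.115 with right skewness 1.0. The t-test alone gives about 0.0265 and 0.033 in the two skewed cases. The actual skewness is unknown, and this is a separate matter from the alpha split, but it rules out an unconditional guarantee.

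It could also be said that enrolment continues whatever the interim shows. Success at either look still counts, so the joint calculation applies. Section 20.2.6 refers to a separate SAP (THRO-STAT-2019-01); its text was not available for this check, so a clarification there cannot be excluded.

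**Conclusion.** The point holds as a minor one. The final cut-off of 0.0212 is the remaining alpha increment, not the final nominal level of the spending design that 20.1 names. At 60/100 the rule's overall one-sided error is about 0.0225 where 0.025 was intended, and the matching nominal level is 0.0238. Over the counts examined (48 or 60 evaluable at the interim, 83 to 125 at the end) the error runs from about 0.022 to 0.0235. The price is about one point of power at n = 100.

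The figures assume the stated evaluable counts, normal theory, and a test that holds its level at each look. They do not support a claim of inflated error from the split, of an underpowered study, or of a wrong N.

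**What to change.** Before final data are seen, in 20.1 and 20.2.2.1, replace the fixed 0.0212 with a rule: the final cut-off is the nominal level computed from the joint distribution of the two looks, given 0.0038 spent at the interim and the actual evaluable counts at each look. Do not write in 0.0238 as a constant, for the reason shown in step 5.

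The cost is about two sentences. The interim level, the enrolment target and the target of 100 evaluable subjects do not change, and N = 83 remains sufficient at any level above 0.0212. The downsides are that the level rests on a normal approximation (t-test error about 0.0251 at n = 100) and that the simple sum bound is given up.

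If the sponsor prefers to keep 0.0212, one sentence in 20.1 is enough: it is the alpha remaining after the interim, used as a conservative p-value cut-off; the overall one-sided error is about 0.022 to 0.0235 depending on evaluable counts, and at most 0.025 provided the test at each look holds its nominal level. Keep that condition in the sentence while 20.2.2.1 lets the data choose the test.

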20.2 Endpoints, Hypotheses, and Analytical Methods

20.2.1 Primary Efficacy Endpoint:

The primary efficacy endpoint is reduction in the chest CT-measured RV/LV diameter ratio assessed by contrast enhanced chest CT from baseline within 48 ± 6 hours of initiation of treatment.

20.2.2 Hypothesis:

The predicate device for Bashir Endovascular Catheter is the EkoSonic Endovascular System (EKOS, Bothell, WA). The SEATTLE II Study reported a reduction in RV/LV diameter ratio of -0.42 ± 0.36 (mean ± SD) in 115 patients who underwent a within-window CT measurement of RV/LV diameter ratio. We hypothesize that RV/LV diameter ratio measured at 48 hours compared with measured ratio at baseline will be reduced on average by more than 20%.

20.2.2.1 Analytical methods: A change score d will be calculated:

$$d = \frac{R_{48} - R_0}{R_0}$$

that expresses the change as a proportion of the baseline value, where R_0 and R_{48} are $\frac{RV}{LV}$ at time 0 and 48 hours post-treatment, respectively. A larger decrease from baseline will result in a change score with a greater magnitude and a negative sign. The change score will be compared to the benchmark value of 20% in a one-sided hypothesis test:

$$H_0: d \geq -0.2$$

$$H_A: d < -0.2$$

The distribution of the change score will be examined to assess whether the normality assumption is met, using both graphical methods (Q-Q plots and histograms) as well as multiple hypothesis tests of normality (Shapiro-Wilk, Kolmogorov-Smirnov, Anderson-Darling, and Cramer-von Mises). Multiple hypothesis testing methods will be employed to assess normality because the choice of the most powerful test depends on the distributional qualities of the data; if the different tests do not result in the same conclusion, more weight will be given to the method that is best suited to the observed distributional qualities of the data (e.g., heaviness of tails). If the data are determined to be normal based on these methods, a t test will be done; if not, a one-sample Wilcoxon

signed rank test (the non-parametric alternative to the one-sample t test) will be done. In addition, the t-test will be presented for the primary endpoint analysis regardless of the normality of the test results.

The test will be performed twice: once at the interim analysis (with $\alpha=0.0038$) and once at the final analysis (with $\alpha=0.0212$). If the p-value is less than α at either analysis, then the test will be considered statistically significant.

20.2.3 Primary Safety Endpoint:

The primary safety endpoint is major bleeding within 72 hours of procedure initiation of r-tPA infusion (the start of the infusion). Bleeding events are classified by the International Society of Thrombosis and Hemostasis (ISTH).

20.2.4 Hypothesis:

The comparator device for Bashir Endovascular Catheter is the EkoSonic Endovascular System (EKOS, Bothell, WA), and results from the study evaluating the safety and efficacy of this device were the basis for the performance goal of 14.9% proposed for this study. The SEATTLE II Study reported a 10% (standard error=2.45%) of moderate to severe bleeding in treated subjects within 72 hours of the treatment initiation. The hypothesis is that the bleeding rate in this study will not exceed $10\% + 2*SE = 14.9\%$. A one-sided, one-sample exact test of a binomial proportion p will be used to test the hypotheses below.

$$H_0: p \geq 0.149$$

$$H_A: p < 0.149$$

The hypothesis test for the primary safety endpoint will not be done at the interim analysis, but only at the end of the study. This test will have a type I error rate of 0.025.

20.2.5 Secondary Endpoints:

Descriptive statistics will be generated for the secondary endpoints listed below. For continuous measures (e.g., Modified Miller Index comparing 48 hours post therapy to baseline), the mean and 95% confidence limits will be calculated, along with the median, standard deviation and range. For frequency outcomes (e.g., device success), results will be reported as the overall frequency of occurrence as well as the percentage of subjects.

1. Device Success: The number of devices with therapy delivered without a device failure.
2. Refined Miller Score as measured on contrast enhanced chest CT (CTA) within 48 hours after the completion of the r-tPA infusion compared to baseline as measured by core lab.
3. All-cause mortality at hospital discharge through 30-day follow-up.

4. SAEs through 30-day follow-up.
5. AEs through 30-day follow-up.
6. UADEs through 30-day follow-up.
7. Recurrent PE through 30-day follow-up.
8. Clinically Relevant Non-Major bleeding: Any sign or symptom of hemorrhage (e.g. more bleeding than would be expected for a clinical circumstance, including bleeding found by imaging alone) that does not fit the criteria for the ISTH definition of major bleeding but does meet at least one of the following criteria:
 - a. Requiring medical intervention by a healthcare professional.
 - b. Leading to hospitalization or increased level of care.
 - c. Prompting a face to face (i.e., not just a telephone or electronic communication) evaluation.
9. Technical procedural complications.
10. Systolic PA pressure measured at completion of infusion after BEC(s) removal and compared to baseline.
11. Cardiac output (CO by Modified Fick calculation in Protocol) and cardiac index (CI) following completion of the r-tPA infusion compared to the baseline.

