race, and gender. Summary statistics (mean \pm standard deviation, minimum, and maximum RV/LV diameter ratio, and the proportion of patients experiencing major bleeding) will be calculated for each demographic subgroup and presented in a table to facilitate group comparisons. Regression models will be fit (linear regression for RV/LV diameter ratio, logistic regression for major bleeding) having each primary endpoint as the dependent variable and demographic group as the independent variable. A separate regression model will be fit for each combination of endpoint and demographic variable to formally test the hypothesis of subgroup differences in each primary endpoint.

Sensitivity analyses will be undertaken to assess the impact of missing data for the primary endpoints. The methods for this analysis are described in detail in Section 8 of the Statistical Analysis Plan (THRO-STAT-2019-01), “Handling of Dropouts and Missing Data.” If subjects become COVID-19 positive after enrollment and during the study, a subgroup analysis will be performed. Refer to Statistical Analysis Plan (SAP) (THRO-STAT-2019-01) for additional details.

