2. OVERVIEW OF EFFICACY

The BashirTM Endovascular Catheter is intended for the controlled and selective infusion of physician-specified fluids, including thrombolytics, into the peripheral vasculature. A First-in-man study was recently completed for the treatment of subjects with submassive pulmonary embolism. The study included administration of r-tPA through the BEC in the form of pulse sprays followed by an infusion over eight hours. Subjects with unilateral embolism were administered a 2mg pulse spray through the basket of the BEC into the pulmonary artery (PA) followed by an infusion of 10mg over approximately eight hours for a total dose of 12 mg. Subjects with bilateral embolisms were administered 2mg pulse sprays into each pulmonary artery followed by an infusion of 5mg of r-tPA into each PA over eight hours for a total of 14mg. Nine subjects were enrolled and treated. After 48 hours the RV/LV ratio decreased from 1.54 ± 0.26 to 0.97 ± 0.06 ($p = .001$: 95% CI = 0.33 to 0.82: 36.7% reduction) as assessed by an independent core lab (Medical Metrics, Houston, TX). Thrombus burden measured by Modified Miller Index as assessed by the independent core lab (Medical Metrics, Houston, TX) decreased from 25.4 ± 5.3 to 16.0 ± 4.0 ($p = .001$: 95% CI = 5.5 to 13.4: 37.1% reduction).

Table 1. Independent Core LAB RV/LV Diameter Ratio

Independent Core Lab RV/LV Diameter Ratio at 48 hours After Completion of r-tPA Infusion By Contrast Enhanced Chest CTA Compared to Baseline				
Baseline	48 hours	Difference (Baseline – 48 hrs)	95% CI of difference	T-test p-value
Mean \pm SD (n) Median [Range]	Mean \pm SD (n) Median [Range]	Mean \pm SD (n) Median [Range]	N=8	
1.54 ± 0.27 (8) 1.48 [1.21-1.98]	0.97 ± 0.06 (8) 0.96 [0.87-1.05]	0.57 ± 0.29 (8) 0.56 [0.18 - 1.02]	$0.33 - 0.82$	0.001

Table 2. Independent Core Lab Modified Miller Index Scores

Independent Core Lab Modified Miller Index Scores at 48 hours After Completion of r-tPA Infusion By Contrast Enhanced Chest CTA Compared to Baseline				
Baseline	48 hours	Difference (Baseline – 48 hrs)	95% CI of difference	
Mean ± SD (n) Median [Range]	Mean ± SD (n) Median [Range]	Mean ± SD (n) Median [Range]	N=9	T-test p-value
25.4 ± 5.3 (9) 28.0 [18.0 – 33.0]	16.0 ± 4.0 (9) 15.0 [11.0 – 22.0]	9.4 ± 5.1 (9) 8.0 [4.0 – 18.0]	5.5 – 13.4	0.001

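### An undefined normality verdict chooses between the t-test and the Wilcoxon test for the primary efficacy claim, so error control for the mean depends on a skew the documents do not give

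*Combined protocol and SAP*

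**What the plan says.** Section 20.2.2 hypothesises that the RV/LV ratio "will be reduced on average by more than 20" per cent. Section 20.1 sizes the trial on the same quantity: "This estimate is based on a one-sided one-sample t-test of mean percent change from baseline to 48-hour assessment". The null and alternative in 20.2.2.1 compare d, the change divided by baseline, with -0.2. They do not say whether d stands for a mean or a median.

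The test is then chosen from the data: "If the data are determined to be normal based on these methods, a t test will be done; if not, a one-sample Wilcoxon" test (signed rank). Normality is judged from Q-Q plots, histograms and four tests (Shapiro-Wilk, Kolmogorov-Smirnov, Anderson-Darling, Cramer-von Mises). If these conflict, "more weight will be given to the method that is best suited to the observed distributional qualities of the data". No significance level is given for them.

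The section adds: "In addition, the t-test will be presented for the primary endpoint analysis regardless of the normality of the test results". Success means a p-value below 0.0038 at the interim or 0.0212 at the final analysis. It is not said which p-value counts if the two tests differ. Section 20.2.6 cites a separate SAP ("Refer to Statistical Analysis Plan (SAP) (THRO-STAT-2019-01) for additional details"), whose text is not in the document reviewed.

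**The concern.** Under the null hypothesis, the signed rank test is a test of the mean only if d is symmetric about its centre. Otherwise it addresses a pseudo-median. Asymmetry is one of the features that would lead the normality checks to reject, so the plan can move away from a test of the mean when the replacement is least suited to the claim.

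The direction of skew matters. If d has a long tail towards little or no reduction (right skew), its median lies below its mean. The signed rank test can then reject although the mean reduction is only 20%. With left skew the rule becomes conservative and loses power.

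The menu of tests is fixed in advance, but the choice within it is not reproducible. Two statisticians with the same data could pick different deciding tests, and the verdict could change between n=60 and n=100. Efficacy success in this single-arm trial rests on this one comparison.

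**Working it through.** **The plan's own figures reproduce.**
- Effect size: (28 - 20)/25 = 0.32. For a one-sided one-sample t-test at alpha 0.0212, the noncentral t gives n = 83 as the smallest size reaching 80% power (0.802; noncentrality 0.32 x sqrt(83) = 2.92). Power at n=100 is 0.872.
- Alpha: section 20.1 takes a "single interim analysis at 60% of total sample, and overall alpha of 0.025 (one-sided"). The O'Brien-Fleming-type spending function gives 2 x [1 - Phi(2.2414/sqrt(0.6))] = 0.0038 at the interim, leaving 0.025 - 0.0038 = 0.0212.

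The sizing is therefore sound, and it belongs to the t-test.

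**False-positive rate for the mean.** Assumptions: d = X - 1, where X = R48/R0 is lognormal with mean 0.80, so the mean reduction is exactly 20%; n=100; 20,000 trials per scenario. The plan's full gate cannot be programmed from its text. Two stand-ins at the 0.05 level were used: Shapiro-Wilk, and Kolmogorov-Smirnov with Lilliefors critical values (0.1135 at n=60, 0.0892 at n=100). Skewness is 3c + c^3 with c = SD/0.80, and the median of X is 0.80/sqrt(1 + c^2). Results at the final look, alpha 0.0212:

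| SD of d | Skewness | Median reduction | Shapiro-Wilk gate | Lilliefors gate | t-test alone |
|---|---|---|---|---|---|
| 12% | 0.45 | 20.9% | 4.0% | 3.3% | 2.4% |
| 15% | 0.57 | 21.4% | 5.0% | 3.9% | 2.5% |
| 20% | 0.77 | 22.4% | 7.2% | 5.8% | 2.8% |
| 25% | 0.97 | 23.6% | 10.2% | 8.5% | 3.0% |

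Over both looks (n=60 at 0.0038, n=100 at 0.0212, gate re-applied at each), against the planned 2.5%:
- SD 12%: 4.2 / 3.5 / 2.7% (Shapiro-Wilk / Lilliefors / t-test).
- SD 25%: 10.6 / 8.9 / 3.3%.
- Normal data: 2.3% for the two-stage rule. Symmetric t with 5 df: 2.4%.

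**Mirrored (left) skew, SD 25%.** The two-stage error falls to 0.4-0.6% at the final look. Power at a true 28% reduction is 90% for the t-test, 71% with the Shapiro-Wilk gate and 75% with the Lilliefors gate.

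**A different skew family.** Shifted gamma, SD 25%, Shapiro-Wilk gate, both looks:

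| Skewness of d | Error, gated | Error, t-test |
|---|---|---|
| +0.5 | 4.7% | 2.7% |
| +1.0 | 11.9% | 3.5% |
| +1.5 | 21.9% | 3.9% |
| -0.5 | 1.3% | 1.8% |
| -1.0 | 0.3% | 1.4% |
| -1.5 | 0.03% | 1.2% |

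At a true 28% reduction, the two tests disagree at the final look in about 10% of trials at skewness +1.0 and 24% at -1.0.

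**Which SD is plausible?** Section 20.1 plans on 25%. Table 1 of Appendix 25.7 (first-in-man, n=8) gives 1.54 ± 0.27 at baseline, 0.97 ± 0.06 at 48 hours and a difference SD of 0.29:
- Covariance = (0.27^2 + 0.06^2 - 0.29^2)/2 = -0.0038.
- Delta method: SD of R48/R0 = (0.97/1.54) x sqrt[(0.06/0.97)^2 + (0.27/1.54)^2 + 2 x 0.0038/(0.97 x 1.54)] = 0.125.

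The low end of the first table is therefore as plausible as the high end. The pilot's mean and median differences (0.57 and 0.56) show no clear skew, but they are absolute changes in eight subjects, not d.

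**The case against.** The rule is written in advance, both tests are named and the t-test is always reported, so a success resting on the Wilcoxon test alone could not be hidden. On this view only a sentence on precedence is missing. Visibility is real, but it does not settle which p-value decides.

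The largest figures stack several assumptions: SD 25%, a lognormal or gamma shape, a tail towards poor response, and one normality test standing in for four tests plus plots. The documents support only the first, as a planning value. This stands: 10% must not be read as this trial's error rate. At SD 12.5% and a true 28% reduction, the gated rule and the t-test never disagreed in 4,000 simulated trials, with power near 100% for both. The inflation matters only if the true mean reduction lies near 20%.

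The hypotheses name neither mean nor median, so a false positive here is relative to the mean. The wording of 20.2.2 and the sizing in 20.1 nevertheless both point to the mean.

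The t-test is not immune to skew: 1.2% to 3.9% over the gamma range, against 0.03% to 21.9% for the gated rule. Fixing it reduces the dependence without removing it.

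The separate SAP may already name the deciding test. If so, the protocol should match it.

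**Conclusion.** The concern holds. A discretionary verdict on the data can replace a test of the mean with one that addresses the mean only under symmetry, and no sentence gives the t-test precedence. This is more than missing detail, because following the rule as written can give the wrong error rate for the stated claim.

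The size is conditional on shape. Under the right-skewed lognormal scenarios, final-look error is 3.3% to 10.2% for the gated rules against 2.4% to 3.0% for the t-test. Under symmetry there is no material inflation. Under left skew at SD 25%, 15 to 19 points of power are lost. The documents give no skewness for d, and the actual gate's error rate cannot be computed from its text. Confidence is medium for those reasons and because the separate SAP could not be read. The point should be fixed before the interim analysis.

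**What to change.** In 20.2.2 and 20.2.2.1, state the target as the population mean of d. Name the one-sided one-sample t-test of mean d against -0.20 as the single deciding test at both looks, whatever the normality checks show. Keep the plots and normality tests as description. Report the Wilcoxon test and a bootstrap confidence interval for the mean as sensitivity analyses that do not decide success. Align the separate SAP.

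The change is to wording: the t-test is already produced and the 83 subjects already rest on it. It would pass through the amendment approvals described in 18.1 and 18.2.

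The statistical cost is some power if d is symmetric with heavy tails. With t (5 df), SD 25% and a 28% reduction (8,000 trials, Shapiro-Wilk gate, final look), power falls from 92% to 87% at n=100 and from 86% to 81% at n=83, still at or above the planned 80%. Under normality there is no loss (87% either way at n=100). Under right skew at SD 25%, apparent power falls from about 95% to about 85%, mainly because the gated rule's error rate is inflated there.
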